3.2 Conditions for Patient Ineligibility

- 3.2.1** Known sulfonylurea treatment within 7 days prior to registration. Sulfonylureas include glyburide/glibenclamide (Diabeta, Glynase); glyburide plus metformin (Glucovance); glimepiride (Amaryl); repaglinide (Prandin); nateglinide (Starlix); glipizide (Glucotrol, GlibeneseR, MinodiabR); gliclazide (DiamicronR); tolbutamide (Orinase, Tolinsase); and glibornuride (Glutril).
- 3.2.2** Diffuse Leptomeningeal metastases.
- 3.2.3** Known allergy to sulfa or specific allergy to sulfonylurea drugs.
- 3.2.4** Use of VEGF inhibitors within 10 days prior to registration.
- 3.2.5** Allergy to gadolinium.
- 3.2.6** Type 1 diabetes mellitus or Type 2 diabetes mellitus actively receiving treatment.
- 3.2.7** Cognitive impairment that precludes a patient from acting as his or her own agent to provide informed consent.
- 3.2.8** Concurrent use of Bosentan.
- 3.2.9** Any major medical illnesses or psychiatric impairments that in the treating physician's opinion will prevent administration or completion of protocol therapy (which may include patients who are elderly, debilitated, or malnourished persons and/or those with renal, hepatic or adrenal insufficiency).
- 3.2.10** Pregnant or breast feeding women due potential damage to the fetus.
- 3.2.11** Inability to undergo MRI or SRS (e.g. due to safety reasons such as presence of a pacemaker).
- 3.2.12** Deemed by the treating physician to be unable to eat regular meals.

3.2.13 Patients currently on beta blockers.

3.2.14 Patient with a known diagnosis of ongoing alcoholism/alcohol abuse.

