1.9 Dose Rationale and Risk/Benefits

No human trials have yet been undertaken to evaluate the use of glyburide in reducing edema in patients with intracerebral malignancies. In Thompson's study, the human dose equivalent of glyburide would be 2.5 mg/d for a 70 kg patient (2). No adverse mouse-related hypoglycemic events were noted with comparative levels of administration. Typical oral doses of glyburide in diabetic patients range from 2.5 to 20 mg/d. The starting dose is usually a single 2.5 mg tab/day, but this can be divided into twice-per-day administrations of 1.25 mg if patients are at risk of developing hypoglycemia. Human trials in ischemic stroke currently use the IV infusion form of glyburide (RP-1127), which has less potential for hypoglycemia and is not dependent on stomach pH. In a current phase I trial evaluating tolerability in healthy volunteers, RP-1127 is given as bolus followed by 72 hour continuous infusion. No serious adverse events have been reported. Two patients with persistent hypoglycemia (at 6 mg/d and 10 mg/d) were discontinued from the study, and one patient (at 6 mg/d) had a transient asymptomatic increase in aminotransferase/alanine aminotransferase levels. In this dose-finding study, 3 mg/d seemed the safest dose to yield therapeutic serum levels while minimizing hypoglycemic risk (12).

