Utilization of infusional glyburide makes sense in patient populations that are critically ill and in an intensive care settings, but trials utilizing oral glyburide are more feasible in outpatient settings. However, no data currently exists proving that oral glyburide is safe in the non-diabetic population. The Glyburide Healthy Volunteer Study is currently enrolling non-diabetic participants who take 1.5 mg/d of glyburide with breakfast. This study is designed to assess potential use of prophylactic glyburide to mitigate TBI in military personnel. As part of the trial, enrollees undergo strenuous physical activity and are monitored for hypoglycemia, dizziness, and/or confusion. Serial glucose monitoring and neuropsychological testing, as well as electrocardiographic and laboratory values, are collected and monitored during the 7 day inpatient study. These results have not yet been reported (13). As such, we aim to undertake a safety study in patients with brain metastases receiving oral glyburide followed by a randomized study to assess the effect of glyburide on peritumoral edema in patients with a high risk of edema increase after stereotactic radiosurgery.

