2.0 OBJECTIVES AND ENDPOINTS

2.1 Primary Objectives

2.1.1 Pilot Portion: To determine the feasibility and safety of administering oral glyburide to non-diabetic patients receiving stereotactic radiosurgery (SRS) for newly diagnosed brain metastases.

2.1.2 Randomized Portion: To determine the number of patients with newly diagnosed brain metastases who have an increase in edema as measured on volumetric FLAIR imaging and the number of patients that require dexamethasone administration (or any corticosteroid administration with the purpose of treating cerebral edema) from the day of SRS* to one month follow-up MRI in the group receiving glyburide versus placebo.

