3.0 PATIENT SELECTION

3.1 Conditions for Patient Eligibility

- 3.1.1** Patients with newly diagnosed brain metastases deemed to be eligible for radiosurgery.
 - 3.1.1.1** Prior whole brain RT and radiosurgery (to areas outside of the newly diagnosed brain metastases requiring radiosurgery) is allowed
- 3.1.2** Subject must have cytologically or histologically confirmed malignancy (this is the original malignancy, not the brain metastases).
- 3.1.3** A diagnostic contrast-enhanced MRI of the brain must be performed within 60 days prior to registration. The contrast-enhancing intraparenchymal brain tumor must be well visualized.
- 3.1.4** History and physical with neurological examination, height, and weight within 14 days prior to registration.
- 3.1.5** No dexamethasone use (or any other corticosteroid use with the purpose of treating cerebral edema) starting 5 days prior to SRS. Patients may be tapered to meet this criterion if deemed safe by the treating physician.
- 3.1.6** Women of child-bearing potential (e.g. not post-menopausal or permanently sterilized women) must have a negative pregnancy test obtained within 14 days prior to registration. This is to prevent potential harm to the fetus by glyburide and radiotherapy.
- 3.1.7** Age \geq 18 years of age.
- 3.1.8** Complete Blood Count (CBC) with differential and a Comprehensive Metabolic Panel (CMP) including Liver Function Tests (LFTs) obtained within 14 days prior to registration and meeting the following requirements:
 - Creatinine Clearance \geq 50 mL/min (by Cockcroft-Gault Equation).

- Total Bilirubin < 1.5 x the upper limit of normal (ULN).
- ALT and AST ≤ 2.5 x ULN.
- Glucose ≥ 80 mg/dL.
- Hemoglobin ≥ 7 mg/dL.
- Absolute Neutrophil Count > 100 cells/mm³.

3.1.9 For the Randomized Portion only:

3.1.9.1 Subject must have at least 2 of the following risk factors:

- Pretreatment Edema/Tumor ratio (≥ 35:1) as contoured on a baseline MRI obtained at most 60 days prior to registration. Patients are allowed to have Whole Brain Radiotherapy (WBRT) or corticosteroid use between the time of pretreatment MRI and SRS (as long as the corticosteroids can be safely tapered at least 5 days prior to the treatment planning MRI and WBRT is at least 4 days prior to registration).
- Greater than 40 pack year history of smoking cigarettes.
- Whole Brain Radiotherapy at least 4 days and no more than 1 year prior to registration.
- RPA Class III.

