5.1 Pilot Portion

10 evaluable patients will be enrolled onto the Pilot Portion. Should there be a glyburide dose reduction, 10 evaluable patients at this lower glyburide dose must be assessed. Inevaluable patients will be replaced.

Patients with brain metastases, who are not taking dexamethasone (or any other corticosteroid with the purpose of treating cerebral edema) within 5 days prior to SRS, after informed consent, will be treated with:

1. Non-Micronized glyburide (1.25 mg orally twice a day (po BID)) should begin 5 days prior to SRS to be taken until the evening dose on the day of the one month follow-up MRI.
2. Radiosurgery will be linac-based and must be initiated at least 5 days after starting glyburide (can be more for patients being treated with linac-based radiosurgery where the MRI may be done within 21 days prior to SRS treatment).

For treatment planning and at the time of the one and three month follow-up appointments, the patient must undergo a brain MRI with and without contrast. T1-weighted, T2, and/or FLAIR MRI of the brain (maximum slice thickness 5mm). FLAIR imaging is preferred. The treatment planning MRI may be done within 21 days prior to SRS treatment only for patients being treated with linac-based radiosurgery where it is not standard of care to complete a MRI on the day of SRS (as it is with gamma knife).

T1 post-gadolinium sequences and FLAIR axial sequences from the treatment planning MRI (see note above regarding linac-based radiosurgery patients) and at the one and three month follow-up appointments will be imported into the Eclipse treatment planning system. On the T1 post gadolinium sequences, the radiation oncologist will contour the enhancing tumor that received the prescribed dose of SRS. Using the FLAIR sequences Eclipse will automatically calculate FLAIR volume using “Region Growing” (Appendix I). The automated contours will be verified and modified as needed by the radiation oncologist.

5.1.1 Patients can only be enrolled after all eligibility criteria are met. The date of registration/enrollment/study entry is considered to be the day the Eligibility Checklist is signed by the verifying physician and should be no later than 5-9 days prior to SRS. Once a patient is enrolled, a unique case number will be assigned.

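### The pilot's safety question is about non-diabetic patients, but untreated type 2 diabetes is not excluded and such patients can count among the 10 who decide the toxicity gate.

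*Combined protocol and SAP*

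**What the plan says.** Section 2.1.1 states the pilot objective: "To determine the feasibility and safety of administering oral glyburide to non-diabetic patients receiving stereotactic radiosurgery (SRS) for newly diagnosed brain metastases". Section 1.9 gives the reason for a safety study first: "no data currently exists proving that oral glyburide is safe in the non-diabetic population".

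The diabetes exclusion in 3.2.6, which applies to both portions, is "Type 1 diabetes mellitus or Type 2 diabetes mellitus actively receiving treatment". Whether the last three words qualify type 2 only or both types, type 2 diabetes without treatment is not excluded.

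The neighbouring criteria do not close the gap. Section 3.1.8 sets a lower glucose limit, "Glucose ≥ 80 mg/dL", with no upper limit and no HbA1c criterion. Section 3.2.1 excludes "Known sulfonylurea treatment within 7 days prior to registration", so someone who stopped a sulfonylurea before that window and takes nothing else for diabetes can pass both.

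On the count, 5.1 says "10 evaluable patients will be enrolled onto the Pilot Portion". Sections 5.3.1 and 9.3.1 apply two rules to those 10: at least 6 with a concerning toxicity, or at least 1 with a serious toxicity, triggers a dose reduction and, at the reduced dose, termination. Nothing caps, stratifies or separately counts patients by diabetes status.

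**The concern.** The population named in the objective and the population admitted by the eligibility criteria differ, and the safety decision rests on only 10 patients. Three of the four toxicity definitions in 5.3.1 involve low blood glucose; the fourth is a death at least possibly attributable to glyburide. If patients with untreated type 2 diabetes were less prone to low glucose on this drug, each one among the 10 would make the gate less likely to fire at a given rate in non-diabetics. The pilot could then clear a dose for a population it had tested only in part.

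The pilot result decides whether the dose is reduced, whether the study is terminated and whether the Randomized Portion opens. Through 5.4.2 it also affects how intensively glucose is checked in that portion.

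**Working it through.** **Inputs.** From the plan: n = 10 (5.1); thresholds of 6 and 1 (5.3.1, 9.3.1); unacceptable true rates of 70% concerning and 30% serious; acceptable rates of 30% concerning and 1% for the serious rule (9.5.1). Assumed, because the documents are silent: k, the number of untreated type 2 patients among the 10, and q, their toxicity rate.

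**Step 1: the plan's own figures.** Exact binomial, one common rate:

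- Serious, 30%: 1 − 0.7^10 = 0.972 (stated 97%).
- Serious rule, 1%: 0.99^10 = 0.904 (stated 90%).
- Concerning, 30%: P(X ≤ 5) = 0.953 (stated 95%).
- Concerning, 70%: P(X ≥ 6) = 0.850 (stated 85%).

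All four reproduce.

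**Step 2: a mixed group, concerning toxicity.** The number of patients with an event is Binomial(10 − k, 0.70) + Binomial(k, q), and the rule fires if the sum is at least 6. For example, take k = 2 and q = 0.30. The two patients contribute 0, 1 or 2 events with probabilities 0.49, 0.42 and 0.09. The other eight must then supply at least 6, 5 or 4, with probabilities 0.552, 0.806 and 0.942. The total is 0.49 × 0.552 + 0.42 × 0.806 + 0.09 × 0.942 = 0.694.

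Probability that the 6-of-10 rule fires:

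| Assumed rate q | k = 0 | k = 2 | k = 3 |
|---|---|---|---|
| 70% (equal risk) | 85% | 85% | 85% |
| 50% | 85% | 78% | 73% |
| 30% (plan's acceptable rate) | 85% | 69% | 59% |
| 0% | 85% | 55% | 33% |

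**Step 3: a mixed group, serious toxicity.** The probability of at least one event is 1 − 0.7^(10−k) × (1 − q)^k. At q = 0, the most extreme case, this is 1 − 0.7^8 = 0.942 for k = 2 and 1 − 0.7^7 = 0.918 for k = 3, against 0.972 for k = 0.

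**Step 4: the route to lighter monitoring.** Section 5.4.2.2 requires no serious toxicity and at most 3 concerning toxicities; 4 or 5 concerning toxicities lead back to the pilot scheme (5.4.2.3). With a 70% rate in non-diabetics, the probability of at most 3 concerning toxicities is 1.1% for k = 0. At q = 0 it is 5.8% for k = 2 and 12.6% for k = 3; at q = 30% it is 3.3% and 5.7%. These are upper bounds, because the requirement of no serious toxicity is ignored.

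**The case against.** The strongest objection is that the documents do not establish even the direction of the effect. They report no hypoglycemia or toxicity rate by diabetes status, and a patient controlled by diet need not have high glucose. The only support is indirect: 1.9 treats non-diabetics as the group with unproven safety, and notes "Typical oral doses of glyburide in diabetic patients range from 2.5 to 20 mg/d". This stands, so the table has to include the row with no change, and the 0% row is the extreme of an unknown range.

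Section 9.5.1 speaks of the true rate with oral glyburide and does not mention diabetes status, so its figures remain approximately right for the average rate in whoever is enrolled. That also stands. The issue is which population they describe.

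A reader might infer that a diluted pilot leads readily to reduced glucose monitoring in the Randomized Portion. The documents do not support this. That step has its own, stricter threshold, and at a 70% rate it stays unlikely (at most 6% with two such patients and 13% with three). Section 5.2 also requires the DSMQAC to review and approve the pilot data before the Randomized Portion starts, so the gate is not purely mechanical.

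Finally, 3.2.6 is common to both portions, so the pilot draws on the same diabetes mix that the Randomized Portion admits. That is a fair point against tightening one portion alone. It does not answer the conflict with 2.1.1.

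**Conclusion.** The mismatch is in the text and needs no assumption. Followed exactly, the plan can count patients outside the stated population of 2.1.1 towards the pilot's safety decision. Even at equal risk, the pilot would not be confined to the patients its objective names.

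A reader might go further and conclude that the gate is demonstrably weakened, or that such patients will take most of the 10 places. Neither follows, since the documents give no rate by diabetes status and no expected number. With two or three such patients and a 70% rate in non-diabetics, the loss for the 6-of-10 rule runs from nothing to a fall from 85% to 55% or 33%. The serious-toxicity rule loses at most 3 or 5 percentage points (97% to 94% or 92%). The arithmetic in 9.5.1 is not in error.

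The point merits a correction before the pilot result is relied on, because the conflict is clear and cheap to remove. The size of its effect is unknown.

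**What to change.** Reconcile 3.2.6 with 2.1.1 in one of two ways:

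1. For the Pilot Portion, make any diagnosis of diabetes, treated or not, an exclusion. This is the cleaner option.
2. Keep such patients eligible, but do not count them among the 10 evaluable for 5.3.1 and 9.3.1, and replace them.

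In either case, state how diabetes status is determined and record it for every patient. Use the same diabetes criterion in the Randomized Portion. If untreated type 2 patients stay eligible there, state that the pilot does not establish safety for them and report their glucose events separately; otherwise that portion would admit, without saying so, a group its pilot did not assess.

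The cost is a change to one eligibility line, a sentence on counting, and the loss of a few otherwise eligible patients. The sample size and the figures in 9.5.1 need no change, and those figures would then refer to the population named in the objective.

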4.0 PATIENT TREATMENT EVALUATIONS

* Due to COVID-19, these study procedures may be conducted remotely, if necessary.

4.1 Pilot Portion

4.1.1 Within 60 days prior to registration

4.1.1.1 Contrast-enhanced MRI of the brain (may be performed at an outside institution).

4.1.2 Within 14 days prior to registration

4.1.2.1 History and Physical with height, weight, neurological exam and corticosteroid use documentation. If using dexamethasone (or any other corticosteroid with the purpose of treating cerebral edema), must implement a plan to have this safely discontinued by 5 days prior to SRS.

4.1.2.2 Complete Blood Count (CBC) with differential and a Comprehensive Metabolic Panel (CMP) including Liver Function Tests (LFTs).

4.1.2.3 Pregnancy test for women of child-bearing potential.

4.1.3 Within 21 days prior to SRS

4.1.3.1 All patients will have a brain MRI with and without contrast suitable for SRS planning. T1-weighted, T2 and/or FLAIR MRI of the brain (maximum slice thickness 5mm). FLAIR imaging is preferred.

4.1.3.1.1 T1 post gadolinium sequence will be imported into the Eclipse treatment planning system and the radiation oncologist will contour the enhancing tumor that received the prescribed dose of SRS.

4.1.3.1.2 FLAIR sequence will be imported into the Eclipse treatment planning system. FLAIR volume will be automatically calculated using “Region Growing” on Eclipse (Appendix I). The automated contours will be verified and modified as needed by the radiation oncologist.

4.1.3.1.3 The MRI should be performed within 21 days prior to SRS treatment. A repeat treatment planning MRI is allowed. This MRI must meet the descriptions stated above in 4.1.3.1

4.1.4 5-9 days prior to SRS

4.1.4.1 Documentation of corticosteroid use/no dexamethasone (or any other corticosteroid with the purpose of treating cerebral edema) use.

4.1.4.2 Give patient a sufficient supply of non-micronized Glyburide tablets (1.25 mg) to be taken orally twice a day (in the morning with breakfast and in the evening with dinner). Missed doses will not be made up. Patient should be instructed to begin glyburide at least 5 days prior to SRS and continue glyburide until the evening dose of the one month post SRS MRI scan.

- 4.1.4.3** Provide patient with study supplies that include a medication/blood glucose log (for recording time of taking glyburide as well as time and value of blood glucose draws), a blood glucose monitor, and handouts for education purposes. The patient will be educated on how to measure and record blood glucose values (see Appendices II-VI).
- 4.1.4.4** Patient should begin fingerstick glucose draws 4 times a day beginning the day of glyburide initiation (in the morning before breakfast [fasting], before lunch, before dinner, and before bed). An additional fingerstick glucose draw will be taken by the nurse/research team member at this visit.

4.1.5 Day of SRS

- 4.1.5.1** Documentation of corticosteroid use/no dexamethasone (or any other corticosteroid with the purpose of treating cerebral edema) use.
- 4.1.5.2** Continued fingerstick glucose draws by patient 4 times a day (in the morning before breakfast (fasting), before lunch, before dinner, and before bed) for at least 1 week after SRS.

4.1.6 1 week after SRS (\pm 3 days)

- 4.1.6.1** Review the patient's blood glucose and medication administration logs.
- 4.1.6.2** CBC with differential and CMP including LFTs.
- 4.1.6.3** Fingerstick Glucose draw by nurse/research team member.
- 4.1.6.4** Adverse event evaluation. If no "*concerning toxicity*" or "*serious toxicity*" (see section 5.3.1), then patient will be instructed to only obtain fingerstick glucose draws once a day (in the morning before breakfast [fasting]) until the day of discontinuation of glyburide.
 - 4.1.6.4.1** If the patient does have a "*concerning toxicity*" or "*serious toxicity*" they must discontinue glyburide (see section 5.3.1) and thus can also discontinue with their fingerstick glucose draws.
- 4.1.6.5** Documentation of corticosteroid usage (record the date of initiation, dose and reason for initiation of any new corticosteroid, especially dexamethasone).

4.1.7 1 month after SRS (- 5 or +10 days)

- 4.1.7.1** Discontinue glyburide (last dose is taken the evening of obtaining the follow-up MRI) and discontinue blood glucose monitoring. Have patient return all remaining (untaken) glyburide tablets.
- 4.1.7.2** Follow-up brain MRI with and without contrast. T1-weighted, T2 and/or FLAIR MRI of the brain (maximum slice thickness 5mm). FLAIR imaging is preferred.
 - 4.1.7.2.1** T1 post gadolinium sequence will be imported into the Eclipse treatment planning system and the radiation oncologist will contour the enhancing tumor that received the prescribed dose of SRS.
 - 4.1.7.2.2** FLAIR sequence will be imported into the Eclipse treatment planning system. FLAIR volume will be automatically calculated using "Region

“Growing” on Eclipse (Appendix I). The automated contours will be verified and modified as needed by the radiation oncologist.

- 4.1.7.3** Follow-up history and physical with neurologic examination and corticosteroid use documentation (record the date of initiation, dose and reason for initiation of any new corticosteroid, especially dexamethasone). A last fingerstick glucose draw will be done by the nurse/research team member at this visit.
- 4.1.7.4** Review and collect the patient’s blood glucose and medication administration logs.
- 4.1.7.5** Adverse event evaluation.
- 4.1.7.6** CBC with differential and CMP including LFTs.

4.1.8 3 months after SRS (- 10 or +14 days)

- 4.1.8.1** Follow-up brain MRI with and without contrast. T1-weighted, T2, and/or FLAIR MRI of the brain (maximum slice thickness 5mm). FLAIR imaging is preferred.
 - 4.1.8.1.1** T1 post gadolinium sequence will be imported into the Eclipse treatment planning system and the radiation oncologist will contour the enhancing tumor that received the prescribed dose of SRS.
 - 4.1.8.1.2** FLAIR sequence will be imported into the Eclipse treatment planning. FLAIR volume will be automatically calculated using “Region Growing” on Eclipse (Appendix I). The automated contours will be verified and modified as needed by the radiation oncologist.
- 4.1.8.2** Follow-up history and physical with neurologic examination and corticosteroid use documentation (record the date of initiation, dose and reason for initiation of any new corticosteroid, especially dexamethasone).
- 4.1.8.3** Adverse event evaluation.
- 4.1.8.4** CBC with differential and CMP including LFTs.

